9.0 TREATMENT/INTERVENTION PLAN

The initial 3 patients will be accrued at 1 or more week intervals and will receive 10mcg of sLe^a in the sLe^a-KLH + 100mcg QS-21 vaccine. Four weeks or more after accrual of the third patient, 3 additional patients may be accrued at 1 week intervals at the full 30mcg sLe^a dose. Four weeks after accrual of the sixth patient, 7 additional patients may be accrued at a rate no greater than two patients per week.

The sLe^a-KLH plus QS-21 vaccines will be injected during weeks 1, 2, 3, 7 and 19 for a total of five injections. They will be stored in a freezer at -80 degrees Centigrade. At the time of administration the vaccine will be thawed and 1ml drawn up into a syringe. Each 1.1 ml vial will contain sLe^a - KLH conjugate 30 mcg (except for the 10 mcg dose) and QS-21 100 mcg per 1 ml of 0.9% saline.

If a second group of 10 patients is evaluated, then the dose of QS-21 in that group will be increased to 150 mcg during weeks 1, 7 and 19 with the dose remaining the same for the other injections. The same precautions will apply to the rate of patient accrual. The initial 3 patients in this group will be accrued at 1 or more week intervals. Four weeks or more after accrual of the third patient, 7 additional patients may be accrued.

All injections will be administered by a trained nurse on an outpatient basis in the Experimental Therapeutics Center at 53rd Street outpatient building. All patients will be observed for 30 minutes after each injection to monitor for acute allergic reactions.

The sites of immunization (arm or thigh usually- buttocks may be used if necessary) will be rotated for each of the immunizations. No injection will be given at a location in which the draining lymph nodes have been removed.

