In most cases, the initial contact with the prospective subject will be conducted either by the treatment team, investigator or the research staff working in consultation with the treatment team. The recruitment process outlined presents no more than minimal risk to the privacy of the patients who are screened and minimal PHI will be maintained as part of a screening log. For these reasons, we seek a (partial) limited waiver of authorization for the purposes of (1) reviewing medical records to identify potential research subjects and obtain information relevant to the enrollment process; (2) conversing with patients regarding possible enrollment; (3) handling of PHI contained within those records and provided by the potential subjects; and (4) maintaining information in a screening log of patients approached (if applicable).

Patients will be recruited for this protocol primarily by their doctor at MSKCC. In addition, patients outside of MSKCC may be aware of this trial from other patients, their local doctors or the National Cancer Information Center.

Once a patient has indicated an interest in participation, he/she will be referred to one of the consenting physicians for further evaluation and discussion of informed consent. If the patient is determined to be eligible, he/she will be registered according to standard MSKCC policy.

Most patients with breast cancer are female, but male patients will not be excluded. Children are excluded from participation in this study since breast cancer is rare in this patient population and therefore toxicity analysis would be of questionable significance.

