8.1 PRETREATMENT EVALUATION

Within 2 weeks of the first injection:

Pregnancy test for premenopausal patients

Within 3 weeks of the first injection:

- Complete history and physical examination
- Complete blood cell count with differential and platelet count (CBC)
- Comprehensive panel (COMP): aspartate aminotransferase (AST), alanine aminotransferase (ALT), albumin, alkaline phosphatase, bilirubin, calcium, creatinine, glucose, total protein, BUN, sodium, potassium, chloride, C02
- CEA, CA153(or BR27-29 or CA27-29)

- Thyroid stimulating hormone (TSH) level
- Urinalysis
- Rectal examination with Hemoccult
- Blood (3 red-top tubes) for immune response studies will be sent to [name] laboratory in [name]. An additional 7.5 ml of blood will be drawn in special tubes to go to [name] lab in Clinical Chemistry for assessment of circulating tumor cells. These blood samples may be drawn on the day of the first injection, but prior to the injection.

Within 4 weeks of the first injection:

Imaging and Diagnostic Studies

- CT scan of the chest/abdomen/pelvis
- Radionuclide bone scan

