10.0 EVALUATION DURING TREATMENT/INTERVENTION

The study evaluation will include parameters to assess the safety of the injections as well as assessments of immunity to sLe^a (Appendix A). Interval safety assessments will include the „Patient Diary“ (Appendix B). Patients will be provided with Appendix A and B. Long term followup will also be maintained to assess toxicity. Although not a primary endpoint, patients will be monitored for any evidence of an anti-tumor effect. Imaging to assess extent of disease will be performed at baseline, then as appropriate for clinical circumstances. Patients with metastatic disease are often evaluated with imaging every 3 months as standard of care. Clinical benefit will also be assessed by physical examination and biochemical studies as outlined below.

SUMMARY TABLE OF EVALUATION

STUDY WEEK VACCINATION	Pre	1	2	3	5	7	9	13	19	23	q3 months ^g
Clinical:											
History	X	X				X		X	X	X	X
Physical Exam	X	X				X		X	X	X	X
CBC w/ Diff	X					X		X	X		
COMP ^b	X				X	X		X	X	X	
CEA, CA153	X										X ^f
TSH	X						X				X
Urinalysis	X										
Pathology Review	X										
Pregnancy Test	X ^a										
Rectal/Hemoccult	X										
Imaging:											
Bone scan	X									X ^f	
CT Scans	X									X ^f	
Response Assessments ^d									X ^f	X ^f	
Anti-sLe ^a											
Immunity:											
Serology (3 RTT)	X	X ^e	X ^e	X ^e	X	X ^e	X	X	X ^e	X	X
CTC Assay	X				X		X		X		X

^a Within 2 weeks of the first injection for a premenopausal patient..

^b Includes total bilirubin, AST, ALT, Sodium, Potassium, Chloride, CO₂, Calcium, Glucose, Total Protein, Albumin, Alkaline Phosphatase, Creatinine, BUN, Bilirubin.

^c Patients may be asked to obtain tissue blocks from previous diagnostic/therapeutic procedures.

^d Overall response assessment includes the measurement of tumor by non-imaging studies such as physical exam.

^e Blood must be drawn before administration of vaccine at week 1,2, 3, 7 and 19. An extra 100ml of heparinized blood may be drawn once (during weeks 9-23) during the course of immunizations depending on the serologic response in individual patients, at the principal investigators discretion, for evaluation of the immune response at the clonal level by hybridoma production.

^f These studies will be performed as standard of care if deemed appropriate by the patient's physician.

^g If feasible, a history and physical examination and serology will be obtained every 3 months until evidence of disease progression.

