10.2 Immunologic Response

Serological response: Three 10 ml red top tubes will be drawn before the first injection, before each subsequent injection and also during weeks 5, 9, 13 and 23. Sera will be evaluated for reactivity against sLe^a in ELISA and/or immunoprecipitation-western blot assays. These assays detect antibodies against sLe^a and confirm identity of the reaction. If serologic reactivity is detected, then additional blood (~10ml) may be drawn at later times after the injections are completed to determine the duration of this response (every 3 months if feasible). An extra 100ml of heparinized blood may be obtained once during the course of immunizations depending on the serologic response in individual patients at the principal investigators discretion, for hybridoma production. This will be used for evaluation of the B-cell response to vaccination at the clonal level by establishment of monoclonal antibodies. This will be performed in collaboration with MabVax Therapeutics, Inc., (San Diego, CA). It will make possible more detailed analysis of the most immunogenic epitopes on sLe^a and more detailed comparison of the avidity of the induced IgG and IgM antibodies than is possible with sera.

T cell response will not be evaluated since this is a carbohydrate antigen and significant T cell response is not anticipated. The immune response analyses will be conducted in the laboratory of [name] under [name] supervision.

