13.1 CRITERIA FOR REMOVAL FROM STUDY

Cessation of treatment

Therapy may be discontinued at any time due to severe unacceptable side effects, dose-limiting toxicities as defined, life-threatening events, patient's non-compliance with the defined treatment plan, the patient becomes pregnant or the patient's request to withdraw consent.

With evidence of recurrent disease or progression of disease, the patient's primary physician will be notified immediately by the protocol investigators. The decision regarding optimal therapy will be made by the patient and the primary physician. The patient may continue on study if the patient's primary physician feels it is acceptable and the only change in therapy is hormone therapy.

The following dose limiting toxicities as evaluated during weeks 1-21 will result in cessation of treatment:

- Grade 2 or greater autoimmune reactions
- Grade 2 or greater allergic reactions (excluding isolated fever and/or flushing)
- Grade 3 or greater toxicity of any kind (excluding grade 3 lymphopenia)

If any of these toxicities occur, no additional patients will be treated except following mutual agreement after discussion with the CBER IND review team.

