14.0 BIOSTATISTICS

This is a pilot study designed to assess the safety and immunogenicity of immunization with sLe^a-KLH plus QS-21 in patients with high risk breast cancer. If immune responses are observed at the 100 mcg level of QS-21 then QS-21 will be escalated to the 150mcg level.

The immunization schedule comprises five injections administered during weeks 1,2,3,7 and 19. The primary endpoint of this trial is to evaluate immunological response to this single antigen and evaluate toxicity. Immunological response for a patient is defined as an antibody response of greater than 1:80 if baseline value was 0 and at least an increase of 8-fold if baseline value is greater than 0. Initially, three patients will be accrued to the study at a dose of 10 mcg of sLe^a. If safe, then ten patients will be accrued to the study at the full 30mcg sLe^a dose. If 6 or more of these 10 patients have an immune response at any time point then an additional 10 patients may be accrued and receive sLe^a-KLH plus QS-21 (at 150mcg) during weeks 1, 7 and 19. This sample size is chosen to minimize the total number of patients who need to be immunized to identify a promising agent with a probability of an immunological response greater than 50% in a series of immunization trials. The error rates of missing a promising agent or selecting a nonpromising agent are set to be at most 10%.³⁶

At the end of the trial a qualitative assessment of the number of responses and frequency of toxicities will be made to determine which dose of QS-21 will be carried forward in future studies.

Severe toxicities are not anticipated. Toxicities will be tabulated according to the NCI CTC version 3.0. Any grade 3 or greater toxicity (excluding grade 3 lymphopenia) or grade 2 or greater allergic/immunologic toxicity (except isolated fever and/or flushing) will result in removal of the patient from the study. Since the above listed toxicities are unexpected, any event of this sort will result in suspension of the study pending further investigation. Descriptive statistics summarizing the antibody responses will be provided for each patient. The length of the study will be approximately 1-2 years.

Circulating tumor cells (CTC) will be evaluated in an exploratory manner to determine whether CTC can be detected in this patient population at baseline and if so whether there is evidence of a decline in those patients who have an immune response.

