16.2 Quality Assurance

Weekly registration reports will be generated to monitor patient accruals and completeness of registration data. Routine data quality reports will be generated to assess missing data and inconsistencies. Accrual rates and extent and accuracy of evaluations and follow-up will be monitored periodically throughout the study period and potential problems will be brought to the attention of the study team for discussion and action.

Random-sample data quality and protocol compliance audits will be conducted by the study team, at a minimum of two times per year, more frequently if indicated.

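### The first-in-human step from 10 to 30 mcg can open before the third patient's week-5 chemistry is in hand and, in the table as extracted, before that patient's first on-study blood count

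*Combined protocol and SAP*

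**What the plan says.** **Timing of the step.** Section 9 enters the first three patients at 10 mcg, at least a week apart. Then: "Four weeks or more after accrual of the third patient, 3 additional patients may be accrued at 1 week intervals", now at 30 mcg. Four weeks is a minimum.

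**Safety condition.** Section 14 states "If safe, then ten patients will be accrued to the study at the full 30mcg sLe^a dose", and Sections 1.0 and 4.2 say the same in substance. None of them names the results, visits or review that would establish safety.

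**Schedule.** The Section 10 table ("SUMMARY TABLE OF EVALUATION"), as extracted, shows:
- chemistry panel (COMP): baseline, then weeks 5, 7, 13, 19 and 23
- blood count (CBC): baseline, then weeks 7, 13 and 19
- history and physical examination: baseline and week 1, then not until week 7

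Section 10.2 confirms in text that serology blood is taken "before each subsequent injection and also during weeks 5, 9, 13 and 23", so a week-5 draw already exists.

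**Halt.** Under Section 13.1 a dose-limiting toxicity stops treatment of further patients until agreement is reached with the CBER IND review team. The list includes "Grade 3 or greater toxicity of any kind (excluding grade 3 lymphopenia").

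**Meaning of accrual.** No section available defines it. Section 7 says "If the patient is determined to be eligible, he/she will be registered according to standard MSKCC policy", and Section 16.2 says "Weekly registration reports will be generated to monitor patient accruals and completeness of registration data"; both suggest registration. Section 8.1 uses a different anchor for its windows: "Within 3 weeks of the first injection".

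**The concern.** Section 3.4 says that sLe^a has not been given to humans before, and Section 11 says that the antigen is present on normal tissues. The three 10 mcg patients are there to show whether a threefold higher dose may start.

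The halt is strict, but it can act only on what has been measured. It exempts grade 3 lymphopenia and no other cytopenia, so a grade 3 fall in another blood count would stop the trial if it were seen. If it causes no symptoms, diaries, the 30-minute observation and the injection visits will not show it. The risk is that some patients receive 30 mcg before a result that, under the plan's own rule, would have stopped dosing.

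**Working it through.** The four-week interval is a design choice, so there is no calculated figure to reproduce. The check is calendar arithmetic.

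**Inputs.** Spacing of at least 7 days and a 28-day minimum (Section 9); injections in weeks 1, 2, 3, 7 and 19 (Section 9); COMP and CBC weeks (Section 10 table as extracted); planned accrual of 1–2 patients a month (Section 14). Week w is taken to start on day 7(w − 1) after first injection, so weeks 1, 2, 3, 5 and 7 start on days 0, 7, 14, 28 and 42. Accrual is first taken as the day of first injection, the reading most favourable to the plan.

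**Formulas.** Step opens = accrual day of patient 3 + 28. Patient 3's first CBC = accrual day of patient 3 + 42.

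| Pace | Patients 1–3 start on day | Step can open | Days since first injection, patients 1 / 2 / 3 | Patient 3's first CBC | 30 mcg injections before it |
|---|---|---|---|---|---|
| Fastest permitted | 0, 7, 14 | 14 + 28 = 42 | 42 / 35 / 28 | 14 + 42 = 56 | patient 4 on days 42 and 49, patient 5 on day 49: 3 in 2 patients |
| 2 per month | 0, 15, 30 | 30 + 28 = 58 | 58 / 43 / 28 | 30 + 42 = 72 | patient 4 on days 58 and 65: 2 in 1 patient |
| 1 per month | 0, 30, 60 | 60 + 28 = 88 | 88 / 58 / 28 | 60 + 42 = 102 | patient 4 on days 88 and 95: 2 in 1 patient |

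At the fastest pace, counting day 56 itself adds one injection each for patients 4, 5 and 6: 6 in 3 patients.

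**Results in hand when the step opens.**
- *Patient 3, any pace:* three injections given, week-5 COMP due that day, no CBC due.
- *Fastest pace:* week-5 COMP is done earlier in 2 of 3 patients. A CBC is done earlier in 0 of 3, since patient 1's falls due on day 42 itself.
- *Planned pace:* a CBC is done in 2 of 3. At 2 per month patient 2's is due on day 15 + 42 = 57, one day before the step, so this count assumes a draw on the first day of week 7.

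**If accrual means registration.** Let d3 and d4 be the delays from accrual to first injection for patients 3 and 4. The gap between their first injections is 28 + d4 − d3 days. Equal delays give 28. The documents give no delays; an assumed difference of −7 to +7 days gives 21 to 35.

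**Can the table be trusted?** The header and the CBC and COMP rows each split into 11 cells, so the rows parse. The response-assessment row agrees with Section 12.3 on week 19. But the circulating-tumor-cell row marks weeks 5, 9 and 19, while Section 4.2 says 5, 13 and 23. Footnote c has no marker in the extracted table, and the vaccination row has merged into the header. The Appendix A calendar is not in the text. The blank CBC cells therefore need confirming against the source table.

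**The case against.** The strongest case for the plan is that the step is already guarded. Four weeks is a floor, safety is a separate condition, and any dose-limiting toxicity stops further treatment. Diaries, 30-minute observation and injection visits at weeks 2 and 3 add to this. Section 3.4 places the greatest earlier toxicity in weeks 2 and 3, which four weeks from first injection covers. Section 11 describes earlier hematologic changes as minimal, transient and unlikely to be due to the vaccine. All of this stands and limits the point to toxicity that shows only in a laboratory test. It does not remove the point: those earlier trials did not contain sLe^a, and none of the protections requires a laboratory result before the step.

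A reader might infer that counting from accrual shortens follow-up. The documents do not support that. The rule runs from accrual to accrual, so a delay applies at both ends and equal delays cancel. The ±7 days is an assumption, and it lengthens the gap as readily as it shortens it. Section 15 was not in the text available, so a definition of accrual cannot be ruled out either.

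A reader might also take the days 0, 7, 14 case as what will happen. It is only the permitted extreme; Section 14 plans slower accrual.

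Finally, the CBC part depends on blank cells in a table that shows damage. If a week-5 mark was lost, that part falls. The missing list of data to review before the step does not depend on those cells.

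**Conclusion.** The point holds as a cheap improvement, with low-to-medium confidence. The 10-to-30 mcg step rests on elapsed time and an undefined safety condition. Even on the favourable reading of accrual, the step can open with patient 3's week-5 chemistry only just due and, subject to the source table, no blood count taken since baseline. In that patient the halt then cannot act on a symptomless laboratory toxicity before 30 mcg dosing starts.

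The exposure is small: two 30 mcg injections in one patient before patient 3's first CBC at the planned pace, or three in two patients at the fastest. These figures assume visits on the first day of each study week and a first 30 mcg injection on the day the step opens.

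It would be wrong to conclude that the escalation is unguarded or that a hematologic risk is known. The documents describe real protections and give no signal of grade 3 cytopenia.

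**What to change.** 1. Check the CBC row against the source table. If it confirms no CBC between baseline and week 7, add one to the existing week-5 draw for the three 10 mcg patients.
2. In Section 9, require review of diaries and of week-5 COMP and CBC from all three before any 30 mcg injection. This gives the safety condition a defined content.
3. For consistency, apply the same requirement to patients 4–6 before the next seven are accrued.
4. Optionally, state the interval from first injection to first injection. This clarifies the rule and has no expected effect when delays are equal.

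With items 1 and 2, week-5 COMP and CBC are in hand for 3 of 3 patients and no 30 mcg injection precedes them.

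**Cost.** Three CBCs, or six with item 3. Visits fall during a week, so the week-5 draw can be on day 28 to 34. With an assumed 3–7 days for results, the hold beyond day 28 is 3 days (28 + 3 − 28) to 13 days (34 + 7 − 28). That is 3 × 1/30 = 0.1 to 13 × 2/30 = 0.9 patient at 1–2 per month. Item 3 could add a second hold of the same length. Sample size, endpoints and dose levels do not change.

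**Limit.** A fall that recovers in the 14 days between the third injection (day 14) and week 5 (day 28) would still be missed.

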10.0 EVALUATION DURING TREATMENT/INTERVENTION

The study evaluation will include parameters to assess the safety of the injections as well as assessments of immunity to sLe^a (Appendix A). Interval safety assessments will include the „Patient Diary“ (Appendix B). Patients will be provided with Appendix A and B. Long term followup will also be maintained to assess toxicity. Although not a primary endpoint, patients will be monitored for any evidence of an anti-tumor effect. Imaging to assess extent of disease will be performed at baseline, then as appropriate for clinical circumstances. Patients with metastatic disease are often evaluated with imaging every 3 months as standard of care. Clinical benefit will also be assessed by physical examination and biochemical studies as outlined below.

SUMMARY TABLE OF EVALUATION

STUDY WEEK VACCINATION	Pre	1	2	3	5	7	9	13	19	23	q3 months ^g
Clinical:											
History	X	X				X		X	X	X	X
Physical Exam	X	X				X		X	X	X	X
CBC w/ Diff	X					X		X	X		
COMP ^b	X				X	X		X	X	X	
CEA, CA153	X										X ^f
TSH	X						X				X
Urinalysis	X										
Pathology Review	X										
Pregnancy Test	X ^a										
Rectal/Hemoccult	X										
Imaging:											
Bone scan	X									X ^f	
CT Scans	X									X ^f	
Response Assessments ^d									X ^f	X ^f	
Anti-sLe ^a											
Immunity:											
Serology (3 RTT)	X	X ^e	X ^e	X ^e	X	X ^e	X	X	X ^e	X	X
CTC Assay	X				X		X		X		X

^a Within 2 weeks of the first injection for a premenopausal patient..

^b Includes total bilirubin, AST, ALT, Sodium, Potassium, Chloride, CO₂, Calcium, Glucose, Total Protein, Albumin, Alkaline Phosphatase, Creatinine, BUN, Bilirubin.

^c Patients may be asked to obtain tissue blocks from previous diagnostic/therapeutic procedures.

^d Overall response assessment includes the measurement of tumor by non-imaging studies such as physical exam.

^e Blood must be drawn before administration of vaccine at week 1,2, 3, 7 and 19. An extra 100ml of heparinized blood may be drawn once (during weeks 9-23) during the course of immunizations depending on the serologic response in individual patients, at the principal investigators discretion, for evaluation of the immune response at the clonal level by hybridoma production.

^f These studies will be performed as standard of care if deemed appropriate by the patient's physician.

^g If feasible, a history and physical examination and serology will be obtained every 3 months until evidence of disease progression.

